1.1 NAME AND DESCRIPTION OF INVESTIGATIONAL PRODUCT

The PSMA Sterile Cold Kit, is a kit comprising all needed materials (lyophilized PSMA for PSMA reconstitution, elution vial for ⁶⁸Ga and ancillary materials for transfer between vials) to perform a room-temperature radiolabelling of PSMA-11 with ⁶⁸Ga. ⁶⁸Ga is not part of the kit and should be provided in the form gallium chloride solution following the requirements of the relevant local regulations. PSMA-11 radiolabelled with ⁶⁸Ga is administered in patients with prostate cancer recurrence after radical treatment.

1.2 RESULTS OF NONCLINICAL STUDIES

A description of the use of PSMA in non-clinical studies can be found in the Investigator's Brochure section 3 (Attachment 1).

1.3 RESULTS OF CLINICAL STUDIES

A description of the use of PSMA in clinical studies can be found in the Investigator's Brochure section 4 (Attachment 1).

2. STUDY OBJECTIVES

2.1 PRIMARY OBJECTIVE

To provide clinical access to ⁶⁸Ga-PSMA-11 PET at the University of Colorado Anschutz until FDA approved PSMA-based PET radiotracers become commercially available. Patients will be monitored for safety.

2.2 SECONDARY OBJECTIVES

To compare the diagnostic impact of ⁶⁸Ga-PSMA-11 PET/CT imaging over current standard of care imaging modalities.

To compare the impact of ⁶⁸Ga-PSMA-11 PET/CT imaging over standard of care imaging on the therapeutic decision (minor and major therapeutic changes) with regards to the number and/or lesion location.

2.3 EXPLORATORY OBJECTIVES

Determine the detection rate of 68Ga PSMA positive extranodal metastatic sites not seen by MRI alone in intermediate- and high-risk prostate cancer patients.

3. ENDPOINTS

3.1.1 Primary Objective

Evaluate the safety and tolerability of ⁶⁸Ga-PSMA-11 using the following primary safety outcome measures: Incidence and nature of AEs and change in clinical laboratory results. Incidence and severity of AEs and adverse events will be estimated with 95% confidence intervals summarized with descriptive statistics.

3.1.2 Secondary Objective

Determine the frequency of positive PSMA PET scans in relation to the PSA value before the PSMA scans and compared to conventional imaging. Results will be summarized descriptively with 95% confidence intervals.

Determine rate of major and minor changes in management by comparing planned management strategy using conventional imaging and executed management strategy incorporating information from ⁶⁸Ga-PSMA-11 PET/CT, regardless of treatment modality.

4. INVESTIGATIONAL PLAN

4.1 SUBJECT SELECTION

4.1.1 Eligibility Criteria

- Histopathologically proven prostate adenocarcinoma
- Age \geq 18 years
- Patients already diagnosed with prostate cancer: Primary Staging: intermediate and high-risk patients per NCCN guidelines
- Biochemical Recurrence: Rising PSA after definitive therapy with prostatectomy or radiation therapy (external beam or brachytherapy):
 - a. Post radical prostatectomy (RP) – AUA recommendation
 - i. PSA greater than or equal to 0.2 ng/mL measured more than 6-13 weeks after RP and confirmed by a second determination of a PSA level of >0.2 ng/mL
 - b. Post-radiation therapy – ASTRO-Phoenix consensus definition
 - i. Nadir + greater than or equal to 2 ng/mL rise in PSA
- Ability to understand a written informed consent document, and the willingness to sign it.

4.1.2 Exclusion Criteria

- Unable to lie flat, still or tolerate a PET/CT scan, or any other condition that would preclude PET/CT imaging.
- Patients with any medical condition or circumstance that the investigator believes may compromise the data collection or lead to a failure to fulfil the study requirements.
- Patients with known hypersensitivity to the active substance or to any of the excipients of the investigational product.

4.2 PATIENT ASSESSMENTS

4.2.1 Symptom assessment pre- and post-imaging

A directed review of symptoms (nausea, fatigue, pain) will be graded against CTCAE to provide baseline evaluation prior to injection and assess for adverse events post-injection.

4.2.2 Change in management surveys.

Referring clinicians will be queried in providing information on how PSMA PET/CT results impacted the clinical management of patients.

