4.3 PET IMAGING

- a) ⁶⁸Ga-PSMA-11 PET preparation: Oral hydration is recommended on the day of the scan. No fasting is required.
- b) Contrast administration: Imaging contrast will not be ordered as part of this study. However, if a clinically indicated diagnostic CT scan is ordered with intravenous iodinated contrast, it can be added at the end of the ⁶⁸Ga PSMA-11 PET imaging.
- c) Voiding: Voiding is recommended immediately before start of the scan.

- d) ⁶⁸Ga-PSMA-11 injection: The intravenously injected dose will be 100-300 MBq (~3-7 mCi) of ⁶⁸Ga-PSMA-11 PET.
- e) PET imaging protocol: Scan coverage will extend from mid-thigh to the base of the skull, starting from the mid-thighs to minimize urinary bladder radiotracer accumulation at the start of PET imaging. At a minimum, 3 minutes per bed position will be used. In certain circumstances, coverage may be extended to the toes.
- f) Patient monitoring: Patients will be monitored for adverse events during injection and uptake phase of the radiotracer.

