6. ADVERSE EVENTS AND REPORTING REQUIREMENTS

6.1 ASSESSMENT OF SAFETY

Pharmacologic effects of ⁶⁸Ga-PSMA-11

⁶⁸Ga-PSMA-11 has been injected for PET imaging in more than 2,616 published patients [11] and the safety profile has been well established. Currently, no serious adverse events related to drug have been reported. This is expected because the mass of compound is minimal, less than 25 micrograms. There is a potential small risk of infection at the site of injection.

Safety evaluation

AEs will be collected during injection and uptake phase (50-100 min) of Ga-68 PSMA-11 PET/CT scan. All safety events will be recorded up to 120 min post injection.

Analyses will be performed for all patients receiving Ga-68 PSMA-11. The study will use the [CTCAE v5.0](#) for reporting of adverse events.

Radiation exposure from PSMA PET/CT imaging

As part of this scan there is radiation delivered from the ⁶⁸Ga and from the low dose CT scan that are performed as part of the PET/CT for attenuation correction and co-registration. Although any exposure to ionizing radiation has the potential to cause some harm to tissue, the radiation exposures in this study are comparable to the low-level exposures associated with common diagnostic procedures such as CT scanning. There remains a low theoretical risk of developing a cancer at some point later in life as a result of the radiation exposure received in this study. This risk is much smaller than the clinical risks posed by the patient's current cancer or the salvage radiation therapy the patient would be receiving. Participants should not father a baby while on this study. Acceptable birth control methods include abstinence, double barrier method, surgically sterilized patient or partner.

In a phase 1 clinical trial (EudraCT: 2016-004971-32) conducted with the PSMA-11 sterile cold kit as Investigational Medicinal Product (IMP), physiological uptake of [68Ga] PSMA-11 was observed in kidneys, urinary bladder, salivary glands and small intestines. The kidneys were the organs receiving the highest absorbed dose. Additional organs with higher dose were the bladder, small intestines, and salivary glands. Estimated radiation absorbed doses in selected organs and tissues are presented in the Table 1 below.

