6.2.3 EXPEDITED REPORTING

Reporting to the Data and Safety Monitoring Committee

If a death occurs during the treatment phase of the study or within 30 days after the last administration of the study drug(s) and it is determined to be related either to the study drug(s) or to a study procedure, the Investigator or his/her designee must notify the DSMC Chair (or qualified alternate) within 1 business day of knowledge of the event. The contact may be by phone or e-mail.

Expedited Reporting to the Food and Drug Administration

If the study is being conducted under an IND, the Sponsor-Investigator is responsible for determining whether or not the suspected adverse reaction meets the criteria for expedited reporting in accordance with Federal Regulations (21 CFR §312.32).

SAE reporting will comply with University of Colorado Anschutz Medical Center SOPs and with local and federal regulations.

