6.2.6 EXPECTEDNESS

Expected Conduct-related AEs

The use of an indwelling cannula for blood sampling and administration of study drug may be accompanied by mild bruising and also, in rare cases, by transient inflammation of the vessel wall. After

initial irritation, the presence of an indwelling cannula is usually painless and hardly noticeable. The same applies to single vein punctures for blood sampling.

Patients may also experience discomfort from lying in the camera, e.g., back pain.

Expected Adverse Drug Reactions

The definition below follows ICH-GCP (see also ICH Guideline for Clinical Safety Data Management: Definitions and Standards for Expedited Reporting):

Adverse drug reaction (ADR)

In the pre-approval clinical experience with a new medicinal product or its new usages, particularly as the therapeutic dose(s) may not be established, all noxious and unintended responses to a medicinal product related to any dose should be considered as ADR. The phrase 'responses to a medicinal product' means that a causal relationship between a medicinal product and an AE is at least a reasonable possibility, i.e., the relationship cannot be ruled out.

Unexpected Adverse Drug Reactions

An unexpected adverse drug reaction is defined as any adverse drug experience, the nature, specificity or severity of which is not consistent with the applicable product information (e.g., investigator's brochure for an unapproved investigational product or Summary of Product Characteristics for an approved product). "Unexpected" as used in this definition refers to an adverse drug experience that has not been previously observed and included in the product information, rather than from the perspective of such experience not being anticipated from the pharmacological properties of the investigational product.

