10. APPENDICES

APPENDIX A: STUDY CALENDAR: SCHEDULE OF ACTIVITIES

	Screening	Day of Scan	Post Scan
Informed Consent	X		
Standard of Care Chart Review	X		
Administration of Ga-PSMA PET Imaging		X	
Safety Monitoring		X	X
Change in management surveys		X	X

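### Injection-site harms that the protocol names are not on the directed symptom review, and no defined procedure looks for them after 120 minutes, so the adverse event rate cannot bound delayed ones

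*Combined protocol and SAP*

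**What the plan says.** **Harms named.** Section 6.1 states: "There is a potential small risk of infection at the site of injection". Section 6.2.6 lists conduct-related events to be expected from the cannula: mild bruising and, "in rare cases, by transient inflammation of the vessel wall". It also mentions discomfort from lying in the camera.

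**What is asked.** Section 4.2.1 provides: "A directed review of symptoms (nausea, fatigue, pain) will be graded against CTCAE". Its purpose is to give a "baseline evaluation prior to injection and assess for adverse events post-injection". No time is set for the post-injection review.

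**What is watched, and for how long.** Section 4.3(f) adds: "Patients will be monitored for adverse events during injection and uptake phase of the radiotracer". The synopsis (Intervention Duration and Safety rows) and 6.1 all end safety recording at 120 minutes after injection.

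**What might come later.** Appendix A ticks Safety Monitoring under both Day of Scan and Post Scan, without saying when or how the second is done. Sections 6.2.1 and 6.2.2 start adverse event (AE) collection and serious adverse event (SAE) reporting at consent and give no end. Section 6.2.3 requires notice to the Data and Safety Monitoring Committee (DSMC), within one business day of knowledge, of a death judged related to the drug or a study procedure, if it occurs in the treatment phase or up to 30 days after the last dose.

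**What is reported.** Sections 3.1.1 and 4.5.1 make AE incidence and severity, with 95% confidence intervals, part of the primary safety outcome. About 100 patients are expected (4.5.3, 6.2.11).

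**The concern.** The harms that the protocol singles out and the questions it puts to patients do not match. Nausea, fatigue and pain are solicited. Infection, bruising and vein inflammation are not, except so far as they hurt.

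Timing adds to this. An infection introduced at injection would not normally declare itself within two hours, so even faultless observation up to 120 minutes could not be expected to show it. Phlebitis or bruising may also first appear after the patient has left. The only entry that could cover this period is the Post Scan tick, and it has no content.

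What is at stake is the meaning of the primary safety estimate. A low or zero incidence would be read as evidence about the named risks, when for the delayed ones it would mainly reflect that no defined step looked for them.

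**Working it through.** The plan states no figure on this point. Section 4.5.3 expressly does without a sample size calculation, so there is nothing to reproduce. The check is mainly of the text.

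**Step 1. Each named harm against the routes that could detect it**

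| Harm | Directed review (4.2.1) | General monitoring to 120 min (4.3(f), 6.1) | Defined step after 120 min |
|---|---|---|---|
| Bruising at the cannula | not listed | yes, if visible by then | none |
| Vein inflammation | only as pain | yes, if visible by then | none |
| Camera discomfort, such as back pain | yes, as pain | yes | none |
| Injection-site infection | only as pain | not to be expected so early | none |

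The definition in 6.2.1 is broad enough to cover all four. It settles what counts as an AE, not who looks or when. The gap is therefore the last row, plus bruising or phlebitis that begins after the window closes.

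**Step 2. Possible later sources of information**

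- Appendix A, Post Scan safety tick: no day, method or content anywhere in the document.
- Section 4.2.2, management survey: addressed to referring clinicians, about management, with no date and no safety question.
- Sections 6.2.1 and 6.2.2: a start (consent), but no end and no later contact.
- Section 6.2.3: a deadline that runs from knowledge of a related death. DSMC reporting of SAEs in 6.1 likewise runs from notification of the sponsor-investigator. Neither says how that knowledge arises.

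**Step 3. The two time spans**

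The recording window is 120 min = 2 h. The period in the death rule is 30 × 24 = 720 h. The ratio is 2/720 = 0.28%.

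**Step 4. What 0/100 would show**

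With n = 100 and no events, the exact two-sided 95% upper limit is 1 − 0.025^(1/100) = 0.0362, or 3.6%.

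This limit applies to the rate of events that are *recorded*. If the true rate is p and a share s of events is recorded, 0/100 bounds p × s at 3.6%, and p itself only at 3.6%/s. Once s falls below about 0.036 that bound exceeds 100% and carries no information. For delayed infection under the described procedures, s is unknown and may be close to zero.

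**Step 5. How many delayed events could be at issue**

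The documents give no rate, so the rates below are assumptions for scale. The expected count is 100p, and the chance of at least one event is 1 − (1 − p)^100.

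| Assumed true rate | Expected in 100 | Chance of at least one |
|---|---|---|
| 0.5% | 0.5 | 39% |
| 1% | 1 | 63% |
| 2% | 2 | 87% |
| 3% | 3 | 95% |
| 5% | 5 | 99% |

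Across this range, a result of 0/100 for delayed events could easily reflect lack of ascertainment instead of absence of harm.

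**The case against.** The strongest case on the other side is that this is a single-dose access protocol. It reports no drug-related serious events in more than 2,616 published patients and a compound mass below 25 micrograms. The named harms are described as small, mild or rare. The 120-minute limit appears three times and looks deliberate, and the incidence is valid for the window it covers. That stands: a short window is a legitimate choice if the result is labelled as such. But the published drug record does not answer a question about the cannula site, and the protocol itself names those harms.

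Three stronger readings are tempting, and the documents do not support them.

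- *That nobody checks patients after the scan.* Appendix A does tick Safety Monitoring under Post Scan. The check is undefined, which is different from absent. Post Scan might even mean later the same day.
- *That all injection-site events would be missed.* Section 4.3(f) is not confined to three symptoms, pain is on the list, and 6.2.1 covers any unfavorable sign. Site reactions seen by 120 minutes can be recorded.
- *That the protocol promises 30-day surveillance and fails to deliver it.* Section 6.2.3 is a notification deadline, limited to related deaths. It does not mention hospitalisation and does not undertake to follow patients.

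Nor would later events come to light only by accident. Staff meetings on each subject's outcomes (6.1), AE entries in the hospital record (6.2.8) and contact with referring clinicians (4.2.2) could each bring one to notice. None is a scheduled search for these harms, so they soften the gap without closing it.

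**Conclusion.** The point holds for delayed injection-site harm. As written, the plan has no injection-site item in its directed review, and no defined procedure would find infection or phlebitis that appears after 120 minutes. The sections on AE collection, SAE reporting, related deaths and the study calendar do not agree on when collection ends, and they name no source of later information.

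The consequence is one of interpretation: 0/100 with an upper limit of 3.6% would describe the first two hours only. How many events are affected cannot be stated, because no rate is given; at assumed rates of 0.5% to 5% it would be 0.5 to 5 patients in 100. The conclusion rests on two assumptions: that infection rarely shows within two hours, and that no separate working document, such as a monitoring plan or case report form, already defines the Post Scan check.

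This is worth correcting because it touches the primary safety outcome and is cheap to put right. It does not invalidate the scan-day AE incidence.

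**What to change.** 1. In 4.2.1, add injection-site findings (pain, swelling, redness, bruising) to the directed review, both before and after injection.
2. In Appendix A, define the Post Scan safety tick as one review of the existing electronic record after day 30, looking for injection-site infection or phlebitis, hospitalisation and death. Do not rely on the management survey for this: it is undated, may fall before day 30, and goes to clinicians who may know nothing of the injection site.
3. Reconcile the synopsis, 6.1, 6.2.1 to 6.2.3 and Appendix A on when AE and SAE collection ends. Without this, a day-30 review would contradict the 120-minute limit.
4. In 4.5.1, report scan-day AE incidence labelled as the 0–120 minute window, and report delayed events separately.

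The cost is a few form items and one chart check per patient, with no added visit. The check may miss events treated elsewhere, so delayed counts should be presented as a minimum. It will also pick up some unrelated disease events, which can be attributed with the causality scale already in 6.2.5.

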4.2.3 Selection and Timing of Dose for Each Subject

No specific patient preparation is required before ⁶⁸Ga-PSMA-11 injection. The imaging agent (Ga-68 PSMA-11) will be administered on an outpatient basis. It will be administered a single time intravenously prior to the PET imaging. The injected dose will be 100 to 300 MBq (~3-7 mCi) of ⁶⁸Ga-PSMA-11.

Following a waiting period of 60 minutes post 68Ga-PSMA-11 administration, patients will be scanned from mid thighs to base of the skull. Images will be acquired with patients in a supine position with their arms raised above their head. If patients cannot raise their arms above the head, the arms will be comfortably positioned and secured by the side of the patient. The goal is to administer this amount of the imaging probe labeled with 2.5 MBq of ⁶⁸Ga per kg body weight with a minimum of 100 MBq (3mCi) and maximum of 300 MBq (7mCi) 68Ga per patient. The typical acquisition time per bed position will be 3 min and the typical number of bed positions is 4.

4.3 PET IMAGING

- a) ⁶⁸Ga-PSMA-11 PET preparation: Oral hydration is recommended on the day of the scan. No fasting is required.
- b) Contrast administration: Imaging contrast will not be ordered as part of this study. However, if a clinically indicated diagnostic CT scan is ordered with intravenous iodinated contrast, it can be added at the end of the ⁶⁸Ga PSMA-11 PET imaging.
- c) Voiding: Voiding is recommended immediately before start of the scan.

- d) ⁶⁸Ga-PSMA-11 injection: The intravenously injected dose will be 100-300 MBq (~3-7 mCi) of ⁶⁸Ga-PSMA-11 PET.
- e) PET imaging protocol: Scan coverage will extend from mid-thigh to the base of the skull, starting from the mid-thighs to minimize urinary bladder radiotracer accumulation at the start of PET imaging. At a minimum, 3 minutes per bed position will be used. In certain circumstances, coverage may be extended to the toes.
- f) Patient monitoring: Patients will be monitored for adverse events during injection and uptake phase of the radiotracer.

4.4 IMAGE ANALYSIS AND INTERPRETATION

A board-certified nuclear medicine physician or nuclear radiologist on-site will interpret the images of the ⁶⁸Ga-PSMA-11 PET/CT scan. Images will be corrected for attenuation and scatter and adjusted for system sensitivity and will provide parametric images in terms of standardized uptake values (SUV) (= MBq found/gm tissue / MBq injected/gm body mass).

PET imaging can be combined with a low-dose CT for attenuation correction, a diagnostic CT (PET/CT), or MRI (PET/MR). Patients may undergo a diagnostic MRI of the prostate, other body parts or a whole-body MRI at the same imaging session as clinically indicated. Contrast material may be administered for the CT or MRI as clinically indicated.

Imaging will be initiated at approximately 60 minutes (45-120 minutes) following administration of the PSMA radiopharmaceutical. At the discretion of the investigator, an additional image of the pelvis may be obtained.

Patients will receive a single dose of ⁶⁸Ga-PSMA-11 and undergo a PET/CT or PET/MRI imaging study. At the time of interpretation of the ⁶⁸Ga-PSMA-11 PET study, the reviewing nuclear medicine physician and/or radiologist will compare the ⁶⁸Ga-PSMA-11 PET findings with the results from previously performed standard-of-care imaging for prostate cancer staging. The presence or absence of sites suspicious for recurrent prostate cancer will be documented. (e.g., prostate bed, lymph nodes, metastases to bone or other organs).

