The primary barrier and challenge facing urologic oncologists is the accurate identification of the source of the rising PSA in the post-prostatectomy setting. Current imaging modalities do not perform with high sensitivity, as far as detecting local or regional recurrence with sensitivity or specificity. This concern is further compounded by the fact that several reports have demonstrated that SRT is more effective in achieving durable PSA suppression when treating patients with lower PSA baseline levels. Based on published guidelines [4-8], SRT is routinely administered to patients with the manifestation of a rising detectable PSA, which is often noted at levels of 0.1-0.5 ng/ml. Especially at these low PSA levels indicative of early relapse, standard imaging studies such as MRI, CT scans, and bone scans are often associated with a low yield of detecting positive imaging findings of < 10% and it is unclear if the more recent use of whole body MRIs provide any further information as to the sites of metastatic disease especially in the setting of early biochemical relapse. Clearly, improved and more sensitive imaging modalities are desperately needed to help identify patients with early disease relapse that is non-metastatic, who would then be suitable candidates for local-regional SRT.

We can hypothesize that the use of PSMA PET imaging will provide information about the site of recurrence that can be used to select patient for SRT and adjust SRT target volumes. It should be noted that especially for high-risk patients with biochemically relapsing disease, routine staging work-up would include bone scan and CT/MRI imaging. Nevertheless, the yield on these studies in the setting of early relapse disease has been low.

Although choline or fluciclovine have improved our ability to detect recurrent and metastatic prostate cancer by interrogating the metabolome that is upregulated in prostate cancer. Specifically, fluciclovine (¹⁸F) uptake is related to increased amino acid transport that has been demonstrated to occur with

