4.5.2 Secondary Objective

Determine rate of overall changes in management by comparing planned management strategy using conventional imaging with executed management strategy incorporating information from ⁶⁸Ga-PSMA-11 PET/CT, regardless of treatment modality.

Analysis: The rate of change in management based on the incorporation of ⁶⁸Ga-PSMA-11 PET/CT results will be expressed as the percentage of total patients imaged in which change in management occurred, regardless of treatment modality. The rate of change in management will also be estimated within each group (initial staging, biochemical recurrence, and pre/post treatment). 95% confidence intervals (CIs) will be used to express precision of the estimates.

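### A separate diagnostic CT or MRI may be added to the PSMA PET session, and the management-change rate has no means of keeping its effect apart from that of the PET

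*Combined protocol and SAP*

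**What the plan says.** Two places allow conventional diagnostic imaging in the PSMA session. Section 4.4: "Patients may undergo a diagnostic MRI of the prostate, other body parts or a whole-body MRI at the same imaging session as clinically indicated". Section 4.3: "if a clinically indicated diagnostic CT scan is ordered with intravenous iodinated contrast, it can be added at the end of the" PSMA PET acquisition. Section 4.3 also makes clear that the study itself orders no contrast, so the contrast CT is a clinical add-on.

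The Background names these same modalities as the conventional standard: "standard imaging studies such as MRI, CT scans, and bone scans".

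The comparator is earlier imaging. At the read, PET findings are set against conventional imaging as follows: "with the results from previously performed standard-of-care imaging for prostate cancer staging" (4.4). In Appendix A the only source of standard-of-care information is a chart review at screening.

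The management endpoint (3.1.2 and 4.5.2) is obtained by "comparing planned management strategy using conventional imaging with executed management strategy incorporating information from" the PSMA PET/CT. The rate is "expressed as the percentage of total patients imaged in which change in management occurred, regardless of treatment modality". It is also estimated within three groups: initial staging, biochemical recurrence, and pre/post treatment. Section 4.2.2 says that referring clinicians will be asked how the PSMA PET/CT results affected management. It describes no item on other imaging done in the same session.

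**The concern.** The secondary objective in 2.2 is the impact of PSMA PET over standard-of-care imaging on the therapeutic decision. The plan that is carried out reflects everything learned in the session. If that session included a new whole-body MRI or contrast CT, the contrast is no longer PSMA PET against conventional imaging. It is PSMA PET plus new conventional imaging against older conventional imaging. A patient whose plan changed because of the MRI alone would raise the PSMA rate.

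The plan does not call for a log of added imaging, a mark showing which modality found a site, a survey item on the source of a change, or a sensitivity analysis. If the source is not captured at the read and in the survey, it may be impossible to recover later. The group rates in 4.5.2 could also be affected unequally if added imaging clusters in one indication.

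**Working it through.** The plan has no figure to reproduce: 4.5.3 waives the sample-size calculation, and the 100 patients are an anticipated number. The check has two parts.

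**1. Can the added imaging enter the rate?**

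- Numerator: patients with any difference between the plan on conventional imaging and the plan carried out (4.5.2).
- Denominator: all patients imaged, with or without added CT/MRI (4.5.2).
- Conventional side: earlier imaging only (4.4), so a same-session CT/MRI never counts there.
- Attribution: 4.2.2 and 4.5.2 refer to PSMA PET/CT results, but do not tell anyone to exclude findings from a diagnostic CT or MRI done in the same session.

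So it can enter, and no step removes it.

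**2. How large could it be?**

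Let p be the change rate due to PSMA PET, m the share of patients with a separate same-session diagnostic CT/MRI, and q the chance that this imaging alone changes the plan in a patient whose PET would not. Then

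observed rate = p + m × q × (1 − p), and inflation = m × q × (1 − p).

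The documents give none of p, m or q; all values below are assumptions.

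| m | q | Inflation, p = 30% | Inflation, p = 50% |
|---|---|---|---|
| 10% | 5% | 0.10 × 0.05 × 0.70 = 0.35 points | 0.25 points |
| 25% | 10% | 0.25 × 0.10 × 0.70 = 1.75 points | 1.25 points |
| 50% | 20% | 0.50 × 0.20 × 0.70 = 7.0 points | 5.0 points |
| 100% | 20% | 1.00 × 0.20 × 0.70 = 14.0 points | 10.0 points |

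The last row is a limiting case, in which every patient has added imaging.

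The only related figure in the documents is in the Background, which puts the yield of standard imaging below 10% at the low PSA levels of early relapse. It is a yield and not a change rate, and it does not cover primary staging or metastatic disease. It therefore does not fix q.

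For scale, the exact (Clopper-Pearson) 95% interval at n = 100 is 21.2% to 40.0% for 30 changes and 39.8% to 60.2% for 50. The half-widths are (40.0 − 21.2)/2 = 9.4 and (60.2 − 39.8)/2 = 10.2 points. In the first three rows the inflation is below the half-width. It exceeds or comes close to it only in the limiting row. The interval describes sampling error and would not widen to cover this bias.

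The formula lets added imaging only add changes. A new MRI could also settle an equivocal PET and prevent a change, so upward bias is likely but not certain.

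**The case against.** The strongest reply is that the wording already points to the PET. The reader compares PET findings, the survey asks about PSMA PET/CT results, and 4.5.2 ties the rate to the incorporation of those results. A careful clinician could leave out a change that came from the MRI. This means that misattribution is possible, not certain. It does not amount to a safeguard, because the report that reaches the clinician may carry both sets of findings and no passage says how to separate them.

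A second reply is that this is an access protocol with a safety primary endpoint, no hypothesis test and descriptive secondary analyses. That stands, and it limits the importance of the point.

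A reader might infer four stronger things that the documents do not support:

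- *That every PET/MRI or PET/CT session is contaminated.* The Synopsis defines the intervention as PET that may be combined with CT or MRI. The anatomical component is part of the test under study. The concern is with a separate diagnostic MRI or contrast CT.
- *That the optional pelvic image is more conventional imaging.* Section 4.4 says "At the discretion of the investigator, an additional image of the pelvis may be obtained" and names no modality. The sentence follows directly on the timing of imaging after the tracer, so a further PSMA PET acquisition is the natural reading.
- *That the detection endpoint is biased in the same way.* Section 3.1.2 counts positive PSMA PET scans. On a plain reading, a lesion seen only on MRI does not make the PET positive.
- *That added imaging falls in the men most likely to have findings.* This is plausible, since it is done on clinical indication, but no passage shows it.

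**Conclusion.** The point holds for the management-change rate and for separate diagnostic CT or MRI added to the PSMA session. Changes that rest only on such imaging may be counted as impact of PSMA PET, and the plan collects nothing that would show how often this happens.

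The size cannot be found from the documents. If 10% to 50% of patients have added imaging, it alone changes the plan in 5% to 20% of those whose PET would not, and the true rate is 30% to 50%, the inflation runs from 0.25 to 7.0 points. It is small if added imaging is uncommon. The endpoint is secondary and descriptive, so this is a worthwhile, inexpensive improvement and does not undermine the study.

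**What to change.** - **Section 4.4:** record for each patient whether a separate diagnostic CT or MRI was added, and mark each suspicious site as PSMA-avid or as seen only on CT/MRI. The exploratory objective in 2.3, on PSMA-positive sites that MRI alone does not show, needs the same record.
- **Section 4.2.2:** add a survey item asking whether the change rested on a PSMA-avid finding or on the added CT/MRI. Include answers for both and for a change resting on absence of PSMA uptake, with a stated rule for counting each.
- **Section 4.5.2:** keep the all-patients rate. Beside it, report the rate of changes resting on a PSMA-avid finding. As a sensitivity analysis, report the rates with and without added diagnostic imaging. Give 95% confidence intervals throughout.

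The headline should not be restricted to sessions without added imaging. Those patients are a selected subset, and their rate would not describe all men imaged. The additional pelvic image should not be classed as conventional imaging.

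The cost is two extra data items (the imaging log with site marks, and the survey question) and a few table rows, with no extra scan or reader. The PSMA-attributed rate may come out somewhat lower than the all-patients rate, and it rests on the clinician's own judgement of cause.
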